Study drug:	Antiplatelets (aspirin, dipyridamole, clopidogrel) vs. Anticoagulants (unfractionated heparin, dalteparin, enoxaparin, tinzaparin, warfarin)
Chief Investigator:	[name]
Study centres/sites:	Sites listed in "Log of Sites" kept by the CADISS Coordinating centre.
Study duration:	The study will end when the last CADISS patient has had their last assessment.
Clinical phase:	Phase IV
Primary Objective:	
To determine the feasibility of a clinical trial comparing antiplatelet therapy with anticoagulation in the acute treatment of patients with cervical artery dissection. Specifically to address whether:
 
 (a) There are sufficient clinical endpoints to provide the power to determine treatment effect (b) Adequate numbers of patients can be recruited.
Study population:	Any patient was has suspected or confirmed dissection on imaging, has symptom onset within seven days and is able to provide informed consent or has a relative/carer/witness to provide assent.
Eligibility Criteria:	
Inclusion criteria:
 
 1) Extra cranial carotid or vertebral artery dissection with symptom onset within 7 days. This includes: 
 a) Ipsilateral TIA or stroke with known date of onset OR b) Ipsilateral Horner's syndrome or neck pain with known date of onset. 
Patients with TIA or stroke in the last 7 days can be entered even if the history of neck pain is >7 days ago. Patients with a recurrent event can be entered as long as the event falls within the 7 day timeframe
 
AND
 2) Imaging evidence of definite or probable dissection on MRI/MRA, CTA or ultrasound (patients can be initially randomised on ultrasound alone but subsequent MR or CTA confirmation is needed)

	
Exclusion criteria:
 
 (i) Intracranial cerebral artery dissection (ii) Symptom onset >7 days (iii) Contraindications to either antiplatelet agents or anticoagulation therapy, including active peptic ulceration or bleeding peptic ulcer within 1 year. (iv) Patient refusal to consent (v) Patients already taking antiplatelets or anticoagulants for other reasons e.g. prosthetic heart valves in whom the treatment cannot be replaced by either antiplatelets or anticoagulants. (vi) Women who are pregnant (vii) Iatrogenic-induced dissection

Study drugs, Dose and Mode of Administration:
	

Duration of Treatment:
	
Patients will be randomised to either antiplatelet agents or anticoagulant agents for three months. The treatment choice is at the discretion of the prescribing physician. After the three month follow-up appointment the patient will receive standard medical treatment and information on treatments at six months and twelve months will be collected by the coordinating centre via telephone.

4: Introduction

4.1 Background

Dissection of the carotid and vertebral arteries is a major cause of stroke in persons <50 years of age, mainly due to embolism from clot sealing the tear. At present physicians treat these patients with anticoagulants or antiplatelet drugs to prevent further stroke, but neither therapy is evidence-based. Anticoagulants may be powerful anti-embolic agents but are also more hazardous than aspirin, and potentially could encourage further dissection. Most published studies are flawed by retrospective data, with no reference to the number of patients in the original study cohort and do not include the critical principles of randomisation and 'blinding' of outcomes.

The only prospective data available⁽¹⁾ suggests that anticoagulants are more effective than antiplatelet agents in reducing further TIA and stroke after dissection, but the numbers were small and lack reliable statistical confirmation. This study was not a randomised controlled trial and therefore may be open to bias in selection of treatment. In addition, it found that most recurrent events occur within the first month and thereafter the number tails off. A total of about 1800 patients would be required for a two armed trial comparing antiplatelet agents with anticoagulants calculated on these data.

Authors of a previous Cochrane review⁽²⁾ reviewing available published literature calculated that a total of about 2800 patients (1400 in each treatment arm) are needed for a blinded randomised trial of anticoagulants vs antiplatelet agents. This would need a major, probably international, study involving over 100 centres, and would be an expensive undertaking. Prior to starting such a study it is important to determine whether this would be feasible. This is particularly important for carotid and vertebral dissection which is a diagnosis frequently missed, at least during the acute phase. Limited natural history outcome data suggests the risk of recurrent stroke and TIA following carotid and vertebral dissection is only markedly raised during the first week to month^(1, 3) and therefore early identification and recruitment of patients is essential if any treatment effect is to be demonstrated.

For these reasons a feasibility study is essential before any large scale clinical trial. Specifically two things need to be determined; firstly, whether sufficient patients can be recruited sufficiently early from participating centres, and secondly, in view of the limited data on the rate of recurrent TIA and stroke in patients with recent dissection, we need more data to obtain a robust estimate of early risk to inform power calculations for a large scale study.

A preliminary informal survey conducted by Clinical Neurosciences, St George's University of London, in association with the Association of British Neurologists, has indicated that at least 27 neurologists/stroke physicians throughout the UK would be interested in collaborating and enrolling consecutive consenting patients into such a study comparing anticoagulation or antiplatelet therapy.

4.2 Investigational Medicinal Product (IMP)

(a) Antiplatelet therapy: Aspirin, dipyridamole or clopidogrel alone or in dual combination.

(b) Anticoagulation with heparin (either unfractionated heparin or a therapeutic dose of low molecular weight heparin) followed by warfarin aiming for an INR in the range 2-3. Local protocols for heparin therapy can be used.

Treatment will be open-label.

Low dose heparin prophylaxis for prevention of DVT is not a contra-indication, but its use should be recorded. Such prophylaxis may be continued after randomisation in the antiplatelet arm at the discretion of the local clinician.

4.3 Pre-clinical data

All drugs used to treat CADISS patients have a known safety profile and are used as part of routine care.

4.4 Clinical data

All drugs used to treat CADISS patients have a known safety profile and are used as part of routine care.

4.5 Study Rationale and risk/benefit analysis

The CADISS Study is a pragmatic trial comparing two regimes: antiplatelet therapy and anticoagulation. Both regimes fall into low risk categories and do not present a higher risk than patients would expect from normal medical care.

4.6 Management of potential study risks

Not applicable to the CADISS Study.

5: Study objectives

5.1 Primary objective

To determine the feasibility of a clinical trial comparing antiplatelet therapy with anticoagulation in the acute treatment of patients with cervical artery dissection. Specifically to address whether:

- (c) There are sufficient clinical endpoints to provide the power to determine treatment effect
- (d) Adequate numbers of patients can be recruited.

This study will lead to a fully powered definitive treatment trial assuming the results of the feasibility phase indicate this is realistic, and particularly that sufficient end-points occur and adequate recruitment can be achieved.

5.2 Secondary objectives

This is a feasibility study and no secondary endpoints have been defined.

6: Trial design

6.1 Overall design

This will be a randomised prospective multicentre study comparing antiplatelet therapy with anticoagulation for patients with carotid and vertebral dissection. Recruitment must be within seven days of onset of symptoms. Patients should not be precluded from randomisation if they are currently treated with antiplatelet or anticoagulant drugs.

6.2 Dosage regimen and rationale

At randomisation, patients will be randomised to either antiplatelets or anticoagulants. The treatment the patient receives will be at the discretion of the prescribing physician and will reflect the treatment options outlined in protocol section 3.2. This drug treatment will continue until the three month follow-up appointment unless the medication of choice needs to be stopped for safety reasons. Following the three month period the patient should be continued on whatever treatment the prescribing physician feels is best for the patient in question.

6.3 Concomitant treatment

CADISS patients will continue on any concomitant medications at the discretion of the prescribing physician. Information on the use of antiplatelets, anticoagulants, antihypertensive agents, hypoglycaemic agents, cholesterol lowering drugs and any thrombolysis treatment will be captured on the entry form and all subsequent follow-up forms.

6.4 Schematic of trial design

Recruitment

1. Review inclusion/exclusion criteria
2. Give patient the Patient Information Sheet or patient's relative/carer the relative/carer information sheet.
3. Obtain Informed Consent (1 original for CRF; 1 copy for patient notes; 1 copy for patient)

Randomisation

1. Telephone Aberdeen randomisation service:
[name] (*Service requires: 4 digit centre ID code and initials*)
2. PI or Sub-I to complete Entry Form and Drug Prescription Form for pharmacy
3. Insert prescription forms into drug chart
4. Fax consent form, entry form and patient contact information sheet to CADISS Office within 24 – 48h
5. Send GP letter

3 Month Follow-Up

1. PI or Sub-I to complete 3 month Follow-Up Form
2. Download all 3 month follow-up images onto CD and send to CADISS Office.
3. Inform patient that at 6 months and 1 year telephone follow-up will be undertaken by coordinating centre (St. George's.)

SAE/SAR/SUSAR

1. PI or Sub-I to complete SAE Reporting Form within 24 h of being notified of event
2. Refer to SAE Reporting SOP
3. Fax initial SAE Report to CADISS Office.
4. CADISS Office, C.I. and Sponsor review SAE Form to classify as either SAE or SUSAR.
5. Complete Follow-Up report within seven days of reporting initial report.
6. All SAEs and SUSARs will need to be followed up until resolution.

Primary or Secondary Clinical Endpoints

1. PI or Sub-I to complete Major Event Form or Drop Out Form.
2. Provide as much clinical information as possible about the clinical event.
3. Fax form and send images (if applicable) to CADISS Office.

7: Eligibility criteria

7.1 Inclusion criteria

- (i) Extra cranial carotid or vertebral artery dissection with symptom onset within the last 7 days

This includes: (a) Ipsilateral TIA or stroke with known date of onset

OR (b) Ipsilateral Horner's syndrome or neck pain with known date of onset

Patients with stroke or TIA within the last 7 days can be entered even if the history of neck pain is > 7 days ago.

Patients with a recurrent event can be entered as long as the event falls within the 7 day timeframe.

and

- (ii) Imaging evidence of definite or probable dissection on MRI/MRA, CTA or ultrasound (patients can be initially randomised on ultrasound alone but subsequent MR or CTA confirmation is needed)

7.2 Exclusion criteria

- (i) Intracranial cerebral artery dissection

- (ii) Symptom onset > 7 days

- (iii) Contraindications to either antiplatelet agents or anticoagulation therapy, including active peptic ulceration or bleeding peptic ulcer within 1 year.

- (iv) Patient refusal to consent

- (v) Patients already taking antiplatelets or anticoagulants for other reasons e.g. prosthetic heart valves in whom the treatment cannot be replaced by either antiplatelets or anticoagulants.

- (vi) Women who are pregnant

- (vii) Iatrogenic-induced dissection.

8: Subject/Patient Recruitment process

Patient recruitment at a site will only commence once the trial team has ensured that the following approval/essential documents are in place:

1. The main REC, and Clinical Trial Authorization (CTA) approval,
2. Final sponsorship and host site approval,
3. Sponsor has conducted the trial initiation procedure.

All sites participating in the trial will also be asked to provide a copy of the following:

1. Signed Clinical Trial Site Agreement (CTSA),
2. Host site (R&D approval)
3. Signed Delegation of Duties and Responsibilities Log.

All subjects who wish to enter the study will be fully screened and consented by the Principle Investigator, or one of the qualified clinicians involved in the study such as Sub-investigator.

9: Study procedures

9.1 Informed consent

Informed consent will be obtained by the Principal Investigator and/or a nominated deputy as recorded on Sponsor's Delegation of Responsibilities Log. Only those members of the study team who have clinical responsibility for the care of patients under the care of the general medical service will be permitted to undertake informed consent. All individuals taking informed consent will have received training in Good Clinical Practice (GCP).

Consent to enter this study will be obtained after a full account has been provided of its nature, purpose, risks, burdens and potential benefits, and the patient has had the opportunity to deliberate. The patient will be allowed to specify the time they wish to spend deliberating, usually up to 24 hours.

Periods shorter than 24 hours will be permitted if the patient feels that further deliberation will not lead to a change in their decision, and provided the person seeking consent is satisfied that the patient has fully retained, understood and deliberated on the information given. This provision has been made with the support of our patient advisory group.

Likewise, periods longer than 24 hours will be permitted should the patient request this. The Investigator or designee will explain that the patients are under no obligation to enter the trial and that they can withdraw at any time during the trial, without having to give a reason.

A copy of the signed Informed Consent Form (ICF) along with a copy of the most recent approved Patient Information Sheet (PIS) will be given to the study participant. The original signed consent form will be retained at the study site (one filed in the medical notes and one filed in the TMF). A copy of the consent form will also be given to the patient.

If new safety information results in significant changes to the risk–benefit assessment, the consent form will be reviewed and updated if necessary. All subjects, including those already being treated, will be informed of the new information, given a copy of the revised consent form and asked to re-consent if they choose to continue in the study.

A witnessed consent form can be used in cases where the patient has understood the study and its relative risks but is unable to provide written consent *i.e.* dysphasia.

In cases where potential participants are deemed incompetent to make a decision during the acute phase following their stroke, advice will be sought from a relative or carer. The relative or carer will be provided with the information sheet for relatives and carers outlining their role and also the requirements of the participant in the study. The relative or carer will be encouraged to ask questions and to discuss the decision with family members, friends and medical professionals. In such cases, the patient's relative or carer may act as the patient's representative and provide assent to the study procedures.

In both cases, the patient will be given the opportunity to discuss and confirm consent or opt out of the study when they are able to independently consent as assessed by the local doctor.

9.2 Randomisation procedure

Randomisation will be via an automated 24 hour randomisation service provided by the University of Aberdeen Health Services Research Unit. The local investigator or delegated person will personally contact this service on [name] along with the trial ID code specific for each centre, known only to the randomisation centre and local investigator. During the call you will also be required to enter the patient's initials. Once this information has been submitted you will receive a randomisation code and a treatment allocation stating either "anticoagulants" or "antiplatelets." Once randomised into the study, all patients will be included in an "intention to treat" analysis.

In the unlikely event of a system failure where you are unable to contact the automated randomisation service you should call the back-up number [name] or perform a manual randomisation by flipping a coin. Please assign a treatment arm to each side of the coin and ask an independent person to flip the coin. Please retain accurate records regarding the event. If you perform a manual randomisation please contact the trial coordinator as soon as possible so that the randomisation details can be passed on to the University of Aberdeen who will update the system retrospectively.

9.3 Emergency unblinding

Not applicable to the CADISS Study.

10: Study Assessments

10.1 Screening assessments

When assessing the patient against the eligibility criteria please carry out the following:

- Review patient's medical history to establish the signs and symptoms associated with suspected dissection. Ensure any relevant signs and symptoms have an onset within seven days.
- Arrange for imaging to confirm dissection.
- Once imaging has been performed review imaging with neuroradiologist to confirm that the dissection does not extend intracranially.
- Ensure patients entered into the study do not have a contraindication to either anticoagulants or antiplatelets. If the patient is already taking anticoagulants or antiplatelets review the indication for which the drug is being taken.
- Discuss the likelihood of pregnancy with any female patients.
- Check for the likelihood of an iatrogenic induced dissection.

10.2 Baseline assessments

When a patient has been randomised, please collect the following information:

- Current cholesterol
- Blood pressure
- Modified Rankin on admission

10.3 Treatment procedure

Patients will be randomised to either antiplatelet or anticoagulation therapy initially for at least 3 months, and thereafter at the discretion of the attending physician.

(a) Antiplatelet therapy: Aspirin, dipyridamole or clopidogrel alone or in dual combination.

(b) Anticoagulation with heparin (either unfractionated heparin or a therapeutic dose of low molecular weight heparin) followed by warfarin aiming for an INR in the range 2-3.

The dose and frequency of IMP should reflect local policy and NICE guidelines.

10.4 Subsequent assessments

This section is not applicable to the CADISS Study.

10.4.1 Follow up assessments

Patients will be seen for follow-up at 3 months post randomisation. Data on outcome and occurrence of recurrent stroke and TIA will be recorded. Repeat imaging with MRA, CTA or intra-arterial angiography should be performed at follow-up to assess vessel recanalisation whenever possible.

In addition, patients will be contacted via telephone at 6 months and 1 year post-randomisation by the central study co-ordinating office at St George's University of London.

To help prevent the loss of participants to follow-up and accurately measure study outcomes, the NHS Information Centre Medical Research Information Service will carry out long-term follow up of study participants. This will include providing relevant information to the Chief Investigator when the following occur during follow up:

- A participant dies
- A participants Primary Care Trust (PCT) changes

Where contact with a subject has been lost and a notification of PCT change has been received, the Chief Investigator will contact the PCT to request details of the participants new General Practitioner (GP). Subsequently the Chief Investigator will then contact the identified GP to request the contact details of the participant or that his contact details are passed onto the participant.

10.5 Summary flow chart of study assessments

Study Procedures	Screening	Following Randomisation: Treatment Initiation	Follow up (3 mnths)	Follow up (6 mnths)	Follow up (12 mnths)
Informed consent	X				
Inclusion/exclusion criteria	X				
Medical history	X				
Demographics	X				
Baseline	X				
Screening	X				
Biochemistry	X Cholesterol Only				
Imaging: MRI dissection views, MRA, CTA, or intra-arterial angiography	X		X		
Telephone call				X	X
Dispensing/Administration of IMP		X			
Concomitant Medication	X		X	X	X

10.6 Methods

10.6.1 Laboratory procedures

Please obtain a cholesterol reading as part of the screening process and document on entry CRF.

10.6.2 Imaging Requirements for study entry

The diagnosis of dissection is based on different modalities in different centres. Centres should use their usual imaging protocol to diagnose dissection. Diagnoses on the basis of MRI with cross-sectional imaging through the artery wall, MRA, CT angiography or intra-arterial angiography are all acceptable. Randomisation on the basis of ultrasound imaging alone is allowable, but in such cases confirmatory imaging by MRI, MRA, CTA or intra-arterial angiography must be performed after study entry.

Patients can be randomised if the local stroke/neurology team agrees that the diagnosis is probable or definite based on clinical features and imaging as above. Hard copies of imaging must be recorded for central reading. The primary analysis will include only those patients judged to have probable or definite dissection on central reading of MRI, MRA, CTA or intra-arterial angiography hard copies by the study neuroradiologist.

MRI, MRA, CTA or intra-arterial angiography should be performed at 3 months to assess vessel recanalisation. These images will also be reviewed centrally.

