10.8 Discontinuation/withdrawal of participants and stopping rules

10.8.1 Withdrawal procedure, treatment suspension and 'stopping rule(s)'

Patients will only be withdrawn from the study if consent is withdrawn. In this circumstance no follow-up data will be collected.

If a patient is randomised and later imaging shows that there is no dissection, the patient should still have all follow-up visits and calls as this is an intention to treat study.

11: IMPs and non-IMPs used in the trial

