15.1 Statistical input in trial design

The data will be analysed by intention to treat using standard statistical tests by the trial statistician. The analyses will compare the treatment groups with respect to the length of time before treatment failure (i.e. occurrence of an outcome event) by means of the Mantel-Haenszel chi-squared test and Kaplan-Meier survival curves. Subgroup analyses will examine risk factors for major outcome events.

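### The protocol gives two unranked populations for the main analysis, centrally confirmed dissections (10.6.2) and intention to treat (9.2, 15.1), so the denominator of the primary event proportion is contradictory

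*Protocol*

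**What the plan says.** Four sections of the protocol bear on who is analysed.

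- **10.6.2 (imaging for study entry):** "The primary analysis will include only those patients judged to have probable or definite dissection on central reading". The reading is of MRI, MRA, CTA or intra-arterial angiography by the study neuroradiologist.
- **9.2 (randomisation):** "Once randomised into the study, all patients will be included in an" intention-to-treat analysis.
- **10.8.1 (withdrawal):** if later imaging shows no dissection, "the patient should still have all follow-up visits and calls as this is an intention to treat study".
- **15.1 (statistics):** "The data will be analysed by intention to treat using standard statistical tests by the trial statistician". No restricted set is named.

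Three further statements set the timing. Entry rests on local judgement: "Patients can be randomised if the local stroke/neurology team agrees that the diagnosis is probable or definite". Randomisation on ultrasound alone is allowed, and for those patients "confirmatory imaging by MRI, MRA, CTA or intra-arterial angiography must be performed after study entry". On masking, 4.2 says: "Treatment will be open-label".

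The primary endpoint (15.2.1) is ipsilateral stroke or death from any cause within 3 months of randomisation. The feasibility phase enters 250 patients (15.3.1).

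**The concern.** A statistician following 10.6.2 leaves out randomised patients whom the central reading does not confirm. One following 9.2 and 15.1 counts them. The protocol does not call either set secondary, and it does not define a modified intention-to-treat population. A statistical analysis plan that took either set as primary would depart from some part of the protocol, so this cannot simply be left to that plan.

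Two things are at stake. The first is the main product of the feasibility phase. Section 15.3.1 relies on the proportion with endpoints to size a definitive trial and describes a decision to continue, extend or stop. That proportion has two candidate denominators.

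The second is possible outcome-dependent exclusion in one subgroup. A patient entered on ultrasound alone who dies before the confirmatory scan has no image of a kind that the central reading accepts. The patient then leaves the restricted set and takes a primary event along. Section 4.1 says that the risk is markedly raised only in the first week to month, which is when such scans could still be pending.

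**Working it through.** **Step 1. Do the sections conflict?**

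| Section | Subject | Set implied |
|---|---|---|
| 10.6.2 | primary analysis | centrally confirmed, probable or definite |
| 9.2 | an intention-to-treat analysis | all randomised, in words |
| 15.1 | analysis of the data | intention to treat, no restriction |
| 10.8.1 | follow-up of patients without dissection | retained, with intention to treat as the reason |

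Only 9.2 says outright that all randomised patients are analysed. Section 15.1 states the principle, and 10.8.1 is about follow-up. Even so, 15.1 is the statistical section and carries no trace of the restriction, and 10.8.1 retains a group that 10.6.2 would remove. The sets differ and are not ranked.

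**Step 2. Whose membership can depend on what happens after randomisation?**

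- *Entered on MRI, MRA, CTA or angiography:* the images precede randomisation. Only the central reading may come later.
- *Entered on ultrasound alone:* the qualifying scan itself comes after entry. No time limit is given, and no rule covers a patient who never has it. Death before the scan removes the patient from the restricted set. So does withdrawal, but there 10.8.1 already ends data collection, so death is the clearer case.

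**Step 3. How much could the denominator matter?** The protocol has no figure to reproduce. The 250 is a fixed target, and the definitive total of the order of 2000 comes without event rate, effect size, alpha or power. What follows is an illustration.

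Assumptions: 10% or 20% of 250 unconfirmed (25 or 50 patients); 5 primary events, all in confirmed patients; definitive trial with 1:1 allocation, halving of risk, two-sided 5%, 80% power.

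Rates: 5/250 = 2.0%; 5/225 = 2.2%; 5/200 = 2.5%.

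Patients per arm, pooled-variance formula, with p̄ = (p1 + p2)/2:

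n = [1.960·√(2p̄(1 − p̄)) + 0.842·√(p1(1 − p1) + p2(1 − p2))]² / (p1 − p2)²

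The observed rate p can enter in two ways: as the control-arm rate (p1 = p, p2 = p/2), or as the average of both arms (p1 = 4p/3, p2 = 2p/3).

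| Denominator | Rate | Total N, p as control rate | Total N, p as two-arm average |
|---|---|---|---|
| 250 | 2.0% | 4638 | 3460 |
| 225 | 2.2% | 4166 | 3106 |
| 200 | 2.5% | 3696 | 2754 |

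Relative fall: (4638 − 4166)/4638 = 10% and (4638 − 3696)/4638 = 20%; likewise (3460 − 3106)/3460 = 10% and (3460 − 2754)/3460 = 20%. The absolute totals depend on the convention; the relative shift does not.

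**Step 4. Is the direction fixed?** No. If one of the 5 events is a death before confirmation, the restricted rate is 4/225 = 1.8%, below 2.0%, or 4/200 = 2.0%, equal to it. In either case 1 of 5 events (20%) is missing from the primary analysis.

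**Step 5. Comparison with sampling error.** The exact 95% interval for 5/250 is 0.7% to 4.6%. The move to 2.2–2.5% lies well inside it.

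**The case against.** The best defence is that the sections can be read together: a restricted primary analysis under 10.6.2, a further all-randomised analysis under 9.2 (which does not call its analysis primary), intention to treat in 15.1 meaning only analysis as allocated, and 10.8.1 securing the data. A set defined by masked reading of images taken before randomisation is also a respectable modified intention-to-treat population. And the numerical effect is small beside sampling error, while both proportions can be reported from the same data.

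Part of this stands. The harmonised reading is possible, but the protocol nowhere states it, and a reader of section 15 alone would not arrive at it. The modified set is defensible for patients imaged before randomisation, but not for ultrasound-only entrants without a rule for missing scans. The point about sampling error is correct; it limits the size of the problem but does not settle which population is primary.

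Four stronger readings are tempting, and the documents do not support them.

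- *That 9.2, 10.8.1 and 15.1 each require analysis of everyone randomised.* Only 9.2 says so in words.
- *That the whole restriction depends on imaging after randomisation.* This is true of ultrasound-only entrants, whose number is not given.
- *That the central reader knows the arm.* The protocol does not say that this reading is masked, but silence does not show that it is unmasked, and an imaging manual or analysis plan may cover it.
- *That a confirmed-only rate overstates what a definitive trial would see.* This needs unconfirmed patients to have fewer events and the later trial to analyse everyone randomised. The documents establish neither, and Step 4 shows that the difference can go the other way.

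**Conclusion.** The point holds as an unresolved contradiction about the primary analysis set, and it should be corrected. It rests on the wording of 10.6.2 against 9.2 and 15.1, with 10.8.1 in support, and needs no numerical assumption. As written, 10.6.2 also lets exclusion depend on outcome for patients entered on ultrasound alone, because death before the confirmatory scan removes a primary event.

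The size cannot be fixed from the documents. Under the assumptions of a 10–20% unconfirmed share and 5 events confined to confirmed patients, the event proportion moves from 2.0% to 2.2–2.5% and the definitive sample size falls by about 10–20%. With events lost before confirmation, the difference shrinks or changes sign. The documents support neither a claim of bias in a known direction nor a claim that randomisation is compromised across the whole trial.

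**What to change.** In 10.6.2, replace the restriction with a statement that the primary analysis includes all randomised patients in the arm allocated, in line with 9.2, 10.8.1 and 15.1. Keep the centrally confirmed set as a named sensitivity analysis. State that the central reading is done without knowledge of allocation or outcome, and report by arm how many patients lack confirmatory imaging.

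If the confirmed set were preferred as primary, the protocol would have to say so in 9.2 and 15.1 too, define which images count, require masked reading, and give a rule for patients who die or withdraw before the scan. That is the longer edit.

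The cost is a short change to 10.6.2. No visit or data item is added, since 10.8.1 already keeps these patients in follow-up. The downside is slight dilution from patients without dissection, which the sensitivity analysis would show.
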